- To describe a proportion of patients who achieved resting HR less than 60 bpm at week 12 of prospective observation.
- To estimate association between the resting HR and achievement of target level of BP at week 12 of prospective observation.
- To describe adherence to the treatment with bisoprolol / perindopril in hypertensive patients with previous MI during the prospective observational period of 12 weeks.
- To describe the tolerability of treatment with bisoprolol / perindopril in hypertensive patients with previous MI during 12 week prospective observation.

Outcome measures

Primary outcome measure:

- Change in the mean systolic and diastolic BP levels at week 12 of prospective observation compared to baseline among patients included in the study.

Secondary outcome measures:

- Change in mean systolic and diastolic BP levels at week 4 of prospective observation compared with baseline.
- Change in number of angina attacks per week at week 4 of prospective observation compared with baseline.
- Change in number of angina attacks per week at week 12 of prospective observation compared with baseline.
- Proportion of patients who were taking lipid lowering therapy (LLT) at week 12 of prospective observation.
- Proportion of patients receiving LLT who achieved target levels of LDL C at week 12 of prospective observation.
- Proportion of patients who achieved SBP \leq 140 mm Hg and DBP \leq 90 mm Hg at week 4 of prospective observation.
- Proportion of patients who achieved SBP \leq 140 mm Hg and DBP \leq 90 mm Hg at week 12 of prospective observation.
- Proportion of patients younger than 65 who achieved SBP \leq 130 mm Hg and DBP \leq 80 mm Hg at week 4 of prospective observation .
- Proportion of patients younger than 65 who achieved SBP \leq 130 mm Hg and DBP \leq 80 mm Hg at week 12 of prospective observation.
- Proportion of patients older than 65 years who achieved SBP \leq 140 mm Hg and DBP \leq 90 mm Hg at week 4 of prospective observation.

- Proportion of patients older than 65 years who achieved SBP≤140 mm Hg and DBP ≤90 mm Hg at week 12 of prospective observation .
- Changes in the mean heart rate (HR) at week 4 of prospective observation compared with baseline.
- Changes in the mean heart rate (HR) at week 12 of prospective observation compared with baseline.
- Proportion of patients who achieved target level of resting HR (55-60 bpm) at week 4 of prospective observation.

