- Proportion of patients who achieved target level of resting HR (55-60 bpm) at week 12 of prospective observation.
- Correlation between the resting HR values stratified by groups and achievement of BP targets at week 12 of prospective observation .
- Proportions of patients with high, medium or low adherence to the treatment with SPC of bisoprolol/perindopril, assessed by MMAS-8 self-reporting questionnaire at week 4 of prospective observation.
- Proportions of patients with high, medium or low adherence to the treatment with SPC of bisoprolol/perindopril, assessed by MMAS-8 self-reporting questionnaire at week 12 of prospective observation.
- Incidence rate of adverse events/ adverse drug reactions and special situations during 12 week observational period of the study.

2 Methods and documentation

Study design and definitions

This is a multi-centre, observational, incomparative, ambispective study, which will retrospectively and prospectively collect clinical and socio-demographic data from medical records of patients with HTN and previous MI initiated with bisoprolol/perindopril SPC in real clinical settings.

Baseline data will be collected retrospectively from medical records of patients with HTN and a history of MI. Baseline data are defined as clinical parameters of interest available in medical records at the nearest date before or at the date of the initiation of SPC with Bisoprolol/ Perindopril.

To be included in the study for further prospective observation a patient should have been administered bisoprolol/ perindopril SPC within first three months before the Index Date. (*Fig.1*).

The Index date is a date when a decision to include a patient in the study for further 12 week prospective observation made by a treating physician after evaluation of recorded data to confirm patient's eligibility for the study.

Therefore, criteria for non-inclusion or inclusion of patients in the study are to be retrospectively evaluated by the treating physician using recorded clinical data available from medical records. Once a treating physician makes decision to include a patient in the study and, in particular, on the prospective observation for 3 months, a visit 0 (inclusion visit) to the clinic for obtaining signed patient's consent to participate in the study should be appointed and made within 1 month from the Index Date.

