Retrospective screening and evaluation of patient's eligibility to inclusion/ exclusion criteria for entering the study allows mitigating a potential risk of deliberative medicine administration within the observational program. Such studies are carried out in case of observational programs when the studied drug is administered in line with indications according to the instruction for its medical use.

Several multicenter, non-interventional, open, incomparable studies have been performed with bisoprolol/perindopril SPC in patients with HTN and coronary heart disease (3,8,13,14). A total of 70 general practitioners and cardiologists from primary care facilities will participate in the program. Each doctor will include about 7-8 patients. In total, it is planned to include at least 500 patients.

Calculation of the sample size

As the present research has an exploratory nature, the study is not intended to prove any hypothesis. In this case, a formal calculation of the sample size is not performed. Moreover, all statistical tests will be performed at a level of statistical significance of 0.05 and a power of 80%.

Given that the study will include patients with any grade HTN, the variability of SBP and DBP levels may be high enough. However, assuming that standard deviations (SDs) at baseline does not exceed 50 mm Hg, a sample of 500 patients will allow achieving a statistically significant difference in BP reduction after 3 months of treatment with bisoprolol/perindopril SPC compared with baseline levels, providing it is 6.3 mm Hg or more.

This non-interventional study has an exploratory nature, so the sample size is not a strict parameter and is recommendatory in nature.

Therefore, in order to obtain a representative population of patients with this particular disease and taking into account the practical aspects of conducting research in daily everyday routine practice, the total sample should consist of at least 500 patients.

Selection of doctors

A total of 70 general practitioners and outpatient cardiologists will participate in this non-interventional study.

Selection of patients

Inclusion criteria

1. Age from 18 to 79 years.
2. Signed informed consent to participate in the study.
3. Stable arterial hypertension with concomitant stable angina pectoris of class I-III according to the Canadian Cardiovascular Society (CCS) classification and a history of myocardial infarction not earlier than 3 months before inclusion in the study

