4. Bisoprolol/perindopril SPC prescription 1-3 months before screening
5. Bisoprolol/perindopril SPC prescription in accordance with Russian SmPC, based on necessity in treatment with bisoprolol/perindopril SPC and separated from the decision to include the patient in the study
6. Clinical parameters of interest (Resting HR; SBP and DBP; frequency of angina attacks per week) are available in medical records for the nearest date before or at the date of the initiation of SPC with Bisoprolol/ Perindopril.

Non-inclusion criteria

1. Hypersensitivity to bisoprolol, perindopril, excipients of the medicine, or other ACE inhibitors.
2. Any contraindication for bisoprolol/perindopril's SPC according to the instruction for medical use
3. CAD, angina pectoris of functional class IV according to the CCS classification (Appendix 1).
4. Chronic heart failure of class III-IV according to the New York Heart Association (NYHA) functional classification of heart failure (Appendix 3).
5. Cerebrovascular diseases (ischemic, haemorrhagic stroke, or transient ischemic attack) within the past 6 months prior to inclusion in the study.
6. A history of revascularization procedure within 3 months prior to inclusion in the study.
7. Hypertrophic obstructive cardiomyopathy.
8. Office BP \geq 180/110 mm Hg on treatment
9. Type 1 diabetes mellitus and decompensated type 2 diabetes mellitus.
10. Bradycardia with a heart rate of less than 60 beats per minute.
11. Atrioventricular block (II-III degree), sinoatrial block, or sick sinus syndrome.
12. Severe bronchial asthma or severe chronic obstructive pulmonary disease.
13. Arterial hypotension (BP less than 100/70 mm Hg).
14. Pregnancy, breastfeeding.
15. Secondary hypertension.
16. Severe decompensated diseases of organs and systems requiring continuous treatment.
17. Current participation in another clinical trial and within 30 days prior to signing informed consent.

Treatment during the study

Treatment with the studied drug

bisoprolol 5 mg + perindopril 5 mg once daily
bisoprolol 5 mg + perindopril 10 mg once daily
bisoprolol 10 mg + perindopril 5 mg once daily
bisoprolol 10 mg + perindopril 10 mg once daily

A minimum dosage may also be prescribed:

bisoprolol 2.5 mg + perindopril 2.5 mg 1 time per day (1/2 tablet of bisoprolol 5 mg + perindopril 5 mg)

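### Patients are chosen up to 3 months after starting the single-pill combination (SPC), with no inclusion order and no count of starters left out, so the results cannot be read as representative of all initiators

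*Combined protocol and SAP*

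**What the plan says.** All places are in the combined protocol and SAP.

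- **Population.** Study design and definitions says that data come from "medical records of patients with HTN and previous MI initiated with bisoprolol/perindopril SPC in real clinical settings". The sample-size section gives representativeness of patients with this disease as a reason for 500 patients.
- **Baseline.** The same design section and inclusion criterion 6 take the nearest record before or on the day of SPC start.
- **Entry.** The Index Date is the day of a decision to include the patient "for further 12 week prospective observation made by a treating physician after evaluation of recorded data". On prior exposure, the design section says "a patient should have been administered bisoprolol/ perindopril SPC within first three months before the Index Date", with no minimum. Inclusion criterion 4 says "Bisoprolol/perindopril SPC prescription 1-3 months before screening". V0, where consent is signed, "should be appointed and made within 1 month from the Index Date".
- **Choice of patients.** "Each doctor will include about 7-8 patients", with 70 doctors. No section gives an order of inclusion, a screening log, or a count of starters not included.
- **BP limits.** Non-inclusion criterion 8 removes office BP at or above 180/110 mm Hg under treatment. Criterion 13 reads "Arterial hypotension (BP less than 100/70 mm Hg" and gives no time point. Table 1 (section 2.7.4) has the criteria checked at screening and again at V0.
- **Tolerability.** The objective is "To describe the tolerability of treatment with bisoprolol / perindopril in hypertensive patients with previous MI during 12 week prospective observation". Adverse-event incidence is likewise limited to the 12-week observation.

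**The concern.** The outcome clock starts before the SPC, but membership of the analysed group is settled after exposure to it. A doctor who picks 7-8 patients from a longer list, after reading their records, may choose on how treatment has gone without intending to. Criteria 8 and 13, when checked at V0, can also remove patients because of their BP on the SPC. Patients who stopped early are likely, though not certain, to be under-represented.

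At stake is what the BP change, target rates, adherence and tolerability results refer to. Without a count of starters not included, a reader of the report cannot tell how far the included patients differ from everyone who was started. A larger sample does not help, because selection of this kind does not shrink as N grows.

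The stated reason for retrospective screening is to prevent prescribing for the sake of the study, and inclusion criterion 5 serves the same end. Neither governs which of the patients already treated are chosen.

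**Working it through.** **1. The plan's own figure.** The sample-size section gives 500 patients, SD at most 50 mm Hg, two-sided 0.05, 80% power and a detectable change of 6.3 mm Hg. With 50 used as the SD of the change:

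delta = SD x (z0.975 + z0.80) / sqrt(n) = 50 x (1.960 + 0.842) / sqrt(500) = 6.26 mm Hg.

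This agrees with 6.3. Recruitment also fits: 70 x 7 = 490 and 70 x 8 = 560. The point is about who enters, not about the arithmetic of N.

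**2. Timing.** Screening and Index Date are taken here as the same time.

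| Source | SPC start to Index Date | SPC start to V0 (add 0-1 month) | SPC start to final visit (add 3 months) |
|---|---|---|---|
| Inclusion criterion 4 | 1-3 months | 1-4 months | 4-7 months |
| Study design and definitions | 0-3 months | 0-4 months | 3-7 months |

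The two lower limits differ and must be reconciled. On either reading, entry can follow weeks or months of exposure that lie inside the baseline-to-week-12 interval.

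**3. Missed starters: illustration.** The documents give no loss rate and no outcome for starters not included, so every input here is assumed. Let the SBP change be -20 mm Hg in those included, let a fraction d of starters be missed, and let their change be c.

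Mean in all starters = (1 - d) x (-20) + d x c. Overstatement of the fall = d x (20 + c).

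| d | c = -10 | c = 0 |
|---|---|---|
| 5% | mean -19.5, overstated by 0.5 | mean -19.0, overstated by 1.0 |
| 10% | mean -19.0, overstated by 1.0 | mean -18.0, overstated by 2.0 |
| 20% | mean -18.0, overstated by 2.0 | mean -16.0, overstated by 4.0 |

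The sign reverses when c is below -20, as it may be for patients left out because their BP fell too low. For scale, the 95% half-width at N = 500 is 1.96 x 15 / sqrt(500) = 1.3 mm Hg if the SD of change is 15 (assumed), and 4.4 mm Hg with the plan's 50.

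**4. Criterion 13: two readings.** Assume on-treatment DBP is normal with mean 80-82 and SD 9-10.

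- *Either limit is enough.* The DBP limit alone removes P(DBP < 70) = Phi((70 - mean) / SD):
  - mean 80, SD 10: 15.9%
  - mean 80, SD 9: 13.3%
  - mean 82, SD 10: 11.5%
  - mean 82, SD 9: 9.1%
- *Both limits are required.* Assume also SBP mean 128-135, SD 11-15, and an SBP-DBP correlation of 0.5. The bivariate normal probability of SBP < 100 together with DBP < 70 is then about 0.05-1.7%.

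The wording does not say which reading applies, and the two differ by roughly an order of magnitude or more.

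**The case against.** The strongest reply is that the protocol claims less than all starters. The Aim speaks of patients treated with the SPC for 12 weeks, the primary outcome is confined to those included, and adherence and tolerability are confined to the prospective period. The study calls itself exploratory and descriptive. This stands in part: the outcome definitions are narrower than the design statement. They do not withdraw that statement or the appeal to representativeness, and a descriptive result still needs a stated population and a denominator.

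Three stronger inferences are tempting, and the documents do not support them.

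- *Doctors already know each patient's BP response, tolerance and persistence when they choose.* The review is described as a check of eligibility, and criterion 6 requires only readings from before or at SPC start. Criterion 8 implies some BP under treatment but does not say which treatment. On-SPC information may well be in the file; no text requires it.
- *The study contains only continuers.* Criterion 4 asks for a prescription, not current use, and Table 1 records current use and reasons for stopping from V0 onwards. Under-representation of early stoppers is likely, because the Aim presumes 12 weeks of treatment and SPC withdrawal triggers the final visit (section 2.7.2). It remains an inference.
- *The BP fall will be overstated.* That requires missed starters to have done worse on average. Patients left out for low BP would have larger falls, and those moved to other drugs may have had similar ones.

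**Conclusion.** The concern holds as a limit on sampling and interpretation. Baseline precedes SPC start, while entry is decided up to 3 months later by the treating doctor, with V0 up to 4 months after start. No inclusion order is set, no count of starters left out is kept, and at least one criterion is applied under treatment. The results describe selected patients some months after initiation and should not be presented as representative of everyone initiated on the SPC.

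The missing order and count, and the open time point of criterion 13, can be read directly from the text. The direction and size of any bias cannot be derived from it. The 0.5-4 mm Hg range holds only under the assumed 5-20% missed and the assumed changes of 0 to -10 against -20 mm Hg. The 9-16% removed by criterion 13 holds only if the DBP limit alone suffices and the assumed DBP distribution is right; far fewer are removed if both limits are required.

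**What to change.** 1. **Inclusion order** (Study design and definitions; section 2.7.4.1 on screening). From the records review already planned, each doctor lists all patients with hypertension and previous MI who were started on the SPC in the defined window, by start date. Eligible patients are invited in that order until 7-8 are included. Reconcile the window between the design section and inclusion criterion 4.
2. **Counts of those not included.** Each doctor reports aggregate, non-identifiable numbers by reason: SPC stopped, each criterion, refused, other. Present them beside the BP, adherence and tolerability results. Take no individual BP data from patients who have not consented unless the ethics committee approves it.
3. **Criteria 8 and 13.** Reconcile and state the time point at which each applies, and whether 100/70 means either limit or both. Leave the thresholds as they are. Report how many patients each criterion removed.
4. **Scope of conclusions.** State that they apply to patients selected up to 3 months after SPC initiation (V0 up to 4 months) who met the criteria at screening and at V0, and not to all initiators.

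The cost is protocol wording, a short log per doctor, slightly slower inclusion and a narrower conclusion. Treatment is unaffected, and the safeguard against prescribing for the study stays in place.

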If the dose adjustment is required, the treating physician can correct the dosage of the drug at any time after the treatment start. The decision on the need to correct the dosage lies upon the treating physician.

In renal failure, it is necessary to adjust the dose depending on the degree of impaired renal function (creatinine clearance).

Concomitant drugs

Due to the non-interventional design of the study, it is allowed to use any concomitant treatment or drugs if it is considered necessary by the treating physician and not contraindicated according to the approved instruction for use. This treatment will be appropriately reflected in the study documentation.

Duration of non-interventional study

It is planned to complete enrolment of patients in this non-intervention study within 6 month.

Follow-up period for each patient will be 3 months.

First patient in is scheduled for Q1 2021

Last patient in is scheduled for Q3 2021

Last patient last visit Q4 2021

Data base lock is scheduled for Q1 2022

Statistical analysis is scheduled for Q2 2022

Clinical study report is scheduled for Q2 2022

Documentation during the non-intervention study

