2.7.1. Documentation folder

Each doctor will be provided with a documentation folder containing a complete set of documents for 7-8 patients + 2 extra sets in case of lost or damage of study documents including:

- One protocol of the observation plan;
- Documents for 7-8 patients (*Patient Informed Consent Form, Case report form (CRF) with 7-8 Adverse event/adverse drug reaction/special situation reporting forms*).
- 2 extra sets in case of lost or damage of study documents (*Patient Informed Consent Form, CRF; Adverse event/adverse drug reaction/special situation reporting forms*)

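### The planned standard errors and two-sided tests make no stated allowance for patients being grouped under 70 doctors; a minor point is that the 50 mm Hg behind the 6.3 mm Hg figure is labelled a baseline SD

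*Combined protocol and SAP*

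**What the plan says.** **Grouping.** Under *Study design and definitions* in section 2, 70 general practitioners and cardiologists take part, and "Each doctor will include about 7-8 patients". The inclusion and non-inclusion criteria "are to be retrospectively evaluated by the treating physician using recorded clinical data available from medical records". Under *Treatment during the study*, "The decision on the need to correct the dosage lies upon the treating physician". Section 2.7.3 has blood pressure taken by Korotkov's method in the doctor's office. Section 2.7.1 organises the paperwork the same way: "Each doctor will be provided with a documentation folder containing a complete set of documents for 7-8 patients".

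**Analysis.** *Statistical analysis* in section 4 calls the analysis descriptive and exploratory. It lists, for each parameter, the number of patients, mean, standard error, minimum and maximum, or the proportion in each category. *Accepted level of significance* adds two-sided tests at 0.05. No test or model is named. No ICC, design effect, random effect or cluster-robust variance appears anywhere in the document.

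**Primary outcome.** Section 1 defines it as "Change in the mean systolic and diastolic BP levels at week 12 of prospective observation compared to baseline among patients included in the study".

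**Sample size.** *Calculation of the sample size* in section 2 says that no formal calculation is made, but that tests are run "at a level of statistical significance of 0.05 and a power of 80"%. It continues: "assuming that standard deviations (SDs) at baseline does not exceed 50 mm Hg, a sample of 500 patients will allow achieving" a significant reduction after three months, "providing it is 6.3 mm Hg or more". No SD of change, follow-up SD or baseline-to-follow-up correlation is given.

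**The concern.** Patients of one doctor share that doctor's judgement of eligibility, dosing habits and office measurement. It is plausible that their changes in blood pressure, heart rate and angina attacks resemble each other more than those of patients under different doctors. The usual formulas for a standard error or a one-sample test treat all 500 patients as independent. If they are not, the formulas count more information than the data hold: standard errors come out too small and tests reject too often. Because the plan is silent, the choice of method stays open until the data have been seen.

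The sample-size sentence raises a smaller question. The primary outcome is a change within the same patients, so its precision depends on the SD of that change. The plan's only SD is labelled as a baseline SD, so a reader cannot tell what 6.3 mm Hg assumes.

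**Working it through.** **Step 1: reproduce 6.3 mm Hg.** Inputs from the plan: n = 500, two-sided 0.05, 80% power, SD 50.

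- Change detectable with 80% power = (1.960 + 0.842) × SD of change / √500. With SD of change 50 this is 2.802 × 50 / 22.36 = 6.26, which rounds to 6.3. The paired t version gives 6.28.
- Other readings do not give 6.3: one-sided 5.56; two independent samples of 500, 8.86; significance alone without power, 1.960 × 50 / 22.36 = 4.38.

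The figure therefore uses 50 as the SD of the within-patient change and treats patients as independent.

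**Step 2: what the baseline label leaves open.** Assume SD 50 at both visits and correlation r. Then SD of change = √(5000 × (1 − r)).

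| r (assumed) | SD of change | 80%-power change, mm Hg | Power at a true 6.3 |
|---|---|---|---|
| 0 | 70.7 | 8.9 | 51% |
| 0.3 | 59.2 | 7.4 | 66% |
| 0.5 | 50.0 | 6.3 | 80% |
| 0.7 | 38.7 | 4.9 | 95% |

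Under equal SDs of 50, the plan's figure corresponds to r = 0.5, which it does not state. These rows put the SD at the plan's ceiling. At an assumed SD of 20 at both visits with r = 0.5, the 80%-power change is 2.802 × 20 / 22.36 = 2.51 mm Hg.

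**Step 3: effect of grouping.** Patients per doctor = 500 / 70 = 7.14. The ICC that matters for the primary outcome is that of the change, because a doctor effect that is identical at both time points cancels. The documents give no ICC, so the values below are assumptions.

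- Design effect = 1 + (7.14 − 1) × ICC
- Ratio of true to ordinary standard error = √(design effect)
- True two-sided error of a nominal 5% test of zero mean change = 2 × (1 − Φ(1.960 / ratio))

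| ICC (assumed) | Design effect | SE ratio | True error | Effective n |
|---|---|---|---|---|
| 0.01 | 1.061 | 1.03 | 5.7% | 471 |
| 0.05 | 1.307 | 1.14 | 8.6% | 383 |
| 0.10 | 1.614 | 1.27 | 12.3% | 310 |

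With 7.5 patients per doctor the SE ratios are 1.03, 1.15 and 1.29, so the exact count matters little.

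**Step 4: check by simulation.** In 40,000 simulated studies per ICC (60 doctors with 7 patients and 10 with 8, so 420 + 80 = 500), the ordinary test rejected a true null in 5.8%, 8.6% and 12.4% of runs. A test with cluster-robust variance by doctor and t on 69 degrees of freedom rejected in 5.1%, 4.8% and 5.2%.

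**Step 5: size in mm Hg.** With an assumed SD of change of 20, an ordinary 95% half-width is 1.96 × 20 / 22.36 = 1.75 mm Hg. Allowing for grouping, it is 1.75 × 1.03 = 1.81 at ICC 0.01 and 1.75 × 1.27 = 2.23 at ICC 0.10.

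**The case against.** The study describes itself as exploratory, tests no formal hypothesis and calls its sample size a recommendation. The ICC is the reviewer's assumption. Harm also requires that the ordinary formulas be used, which the plan neither says nor rules out. If blood pressure falls by much more than its standard error, the primary test will reject under either method, and Step 5 shows that the absolute widening may be well under 1 mm Hg.

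All of this is fair, and it limits the weight of the point. It does not remove it. A standard error is itself a statement of precision, and the plan commits to standard errors and to tests. The same issue reaches heart rate, angina attacks and the target-pressure proportions, where the margins may be narrower.

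Four stronger readings are tempting, and the documents do not support them:

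- **That 6.3 is an arithmetic error.** It reproduces at 6.26. Read simply as an observed reduction that would reach significance, the sentence holds even at equal SDs of 50 and zero correlation, with independent patients (1.960 × 70.7 / 22.36 = 6.20).
- **That 500 patients are too few.** The plan gives 50 as a ceiling. With independent patients, 6.3 keeps 80% power for any SD of change up to 6.3 × 22.36 / 2.802 = 50.3, which at zero correlation and equal SDs means an SD of 50.3 / √2 ≈ 35.6 at each visit. The stated grounds for 500 are representativeness and practicality.
- **That the estimated effect is biased.** Ignoring doctor does not bias the mean changes or the proportions; it affects only their stated uncertainty.
- **That the database lacks a doctor code.** Section 5.1 lists a unique number, age and gender, but it is a privacy statement and not an inventory of case report form fields. The form is not among the documents, so this is something to check, not a gap that has been shown.

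**Conclusion.** The point holds as a gap in the analysis specification. The plan promises standard errors and two-sided 0.05 tests for patients grouped under 70 doctors, and nowhere says how that grouping is handled. If outcomes correlate within doctor and ordinary formulas are used, the true standard error exceeds the reported one by about 3% to 27%, and a nominal 5% test of a mean change errs about 5.7% to 12.3% of the time, over assumed ICCs of 0.01 to 0.10. At the low end the effect is negligible; at the high end it is worth correcting. The range rests on the assumed ICCs and on roughly equal numbers of patients per doctor.

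The sample-size sentence needs only a clarification. As an 80%-power figure, 6.3 mm Hg requires an SD of change of 50 (with SD 50 at both visits, a correlation of 0.5) and independent patients. Relabelling it changes nothing that the study does.

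**What to change.** 1. In *Statistical analysis* (section 4), state that standard errors and tests for the primary blood pressure change and the main secondary outcomes (heart rate, angina attacks, target-pressure proportions) will use a method that accounts for doctor. Cluster-robust variance with doctor as the cluster, with t on doctors minus 1 degrees of freedom, is one option; a model with a random doctor effect is another. Name the choice before the data are analysed.
2. Check that each patient's record in the database carries a coded doctor identifier, and add one if it does not. The per-doctor folders should make this easy at data entry.
3. In *Calculation of the sample size* (section 2), relabel 50 mm Hg as the SD of the within-patient change, or keep it as a baseline SD and state the assumed correlation. Describe 6.3 mm Hg as the true mean change detectable with 80% power at two-sided 0.05, assuming independent patients.

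The cost is a sentence or two in each of two sections, at most one coded field per patient, and one analysis option. No extra patients or visits are needed. The downside is somewhat wider error bars.
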